### **C. TREATMENT PLAN**

#### **C.1. Study design**

We propose a single-site 12-week double-blind placebo-controlled pilot study of CBDV manufactured by GW Pharmaceuticals as GWP42006 in 36 children and young adults aged 5 to 30 diagnosed with PWS and have a high level of irritability ( $\geq 18$  on the ABC-I). Although not expected in this population, patients who test positive for marijuana use will be excluded from the study. PWS diagnosis will be confirmed using patient medical records and previous genetic testing. Please see **Table 1** for the Schedule of Events. Albert Einstein College of Medicine-Montefiore Medical Center will be the study site. Participants in the study will be selected from the PWS network, and the site will use their current patient databases in addition to local advertising for recruitment.

#### **C.2. Subject Selection**

##### **Inclusion Criteria**

1. Male or Female outpatients aged 5 to 30 years.
2. Diagnosis of PWS confirmed by genetic testing and patient medical records and history.
3. Stable pharmacologic, educational, behavioral and/or dietary interventions for 4 weeks prior to the study start, and for the duration of the study.
4. Have a physical exam and laboratory results that are within the norms for PWS
5. Presence of a parent/caregiver/guardian that is able to consent for their participation and complete assessments regarding the patient's development and behavior throughout the study. Child Assent will be obtained if the subject is 7 years of age or older and has the mental capacity to understand and sign a written assent form and/or give verbal assent.
6. Score on the Clinical Global Impression Scale Severity (CGI-S)  $\geq 4$  (moderate severity) at baseline.
7. Score of  $\geq 18$  on the Aberrant Behavior Checklist-Irritability (ABC-I) at baseline.
8. Agree not to drive or operate machinery.

##### **Exclusion Criteria**

1. Exposure to any investigational agent in the 30 days prior to randomization.
2. Prior chronic treatment with CBD or CBDV.
3. Positive testing for THC or other drugs of abuse via urine testing at the screening visit or baseline visits upon repeat confirmation testing.
4. History of Drug Abuse Disorder including Cannabis Use Disorder
5. A primary psychiatric diagnosis other than PWS, including bipolar disorder, psychosis,

- schizophrenia, PTSD or MDD. These patients will be excluded due to potential confounding results.
6. A medical condition that severely impacts the subject's ability to participate in the study, interferes with the conduct of the study, confounds interpretation of study results or endangers the subject's well-being (including but not limited to hepatic or renal impairment and cardiovascular disease).
  7. Known or suspected allergy to CBDV or excipients used in the formulation (i.e. sesame).
  8. ***Clinical indications of*** renal, pancreatic, or hematologic dysfunction as evidenced by values above upper limits of normal for BUN/creatinine, values twice the upper limit of normal for serum lipase and amylase, platelets  $<80,000 /\text{mcL}$ ,  $WBC < 3.0 \times 10^3 /\text{mcL}$ , or  $> 2 \times \text{UNL}$  values of AST or ALT.
  9. ECG abnormality at baseline screening or clinically significant postural drop in systolic blood pressure at screening. If the initial screening ECG shows a QTcB of greater than 460 msec, then 2 additional ECGs will be conducted in the same sitting, 5 minutes apart. If not recognized at screening, then a full triplicate repeat showing an average QTcB of 460 msec or less to meet all inclusion/exclusion criteria
  10. Female subjects who are pregnant will be excluded from the study. If a female subject is able to become pregnant, she will be given a pregnancy test before entry into the study. Female subjects will be informed not become pregnant while taking CBDV. Female subjects must tell the investigator and consult an obstetrician or maternal-fetal specialist if they become pregnant during the study.

### C.3. Description of Study Treatments

#### C.3.1. Study Drug Description

CBDV is obtained from the *Cannabis sativa* L. plant by extraction and purification to produce an extract known as the botanical drug substance (BDS). The BDS is purified by crystallization to yield the CBDV active substance. We will use GW Pharmaceutical's formulation of CBDV, GWP42006. GWP42006 is an oral solution containing 50 mg/mL purified CBDV, dissolved in the excipients sesame oil and anhydrous ethanol with added sweetener (sucralose) and strawberry flavoring and  $\beta$ -carotene. Placebo oral solution contains matching excipients. Purified CBDV contains a negligible quantity (less than 0.2%) of THC.

#### C.3.2. Study Drug Supply

CBDV will be supplied by GW Pharmaceuticals as a 50 mg/mL oral solution. GW will export CBDV as a formulated drug product directly to [name] or through approved 3rd party. GW Pharmaceuticals will supply study drug and placebo at no cost to the study site for the duration of the study.

#### C.3.3. Study Drug Dosing

Enrolled patients will receive a weight-based dosing of 10 mg/kg/day of CBDV (weight-based, up to 800 mg/day) or placebo for 12 weeks, administered bid. The IMP will be administered with food.

##### I. Titration Phase

The total planned titration phase will be 4 weeks as tolerated up to a maximum of 10mg/kg/day up to 800 mg/day per day total.

Proposed schedule:

Week 1: 2.5 mg/kg/day

Week 2: 5 mg/kg/day week

Week 3: 7.5 mg/kg/day week

Week 4: 10 mg/kg/day week

## II. Maintenance Phase (Weeks-4-12)

Subject will be maintained on maximum tolerated titrated dose up to 10 mg/kg/day (given as 5 mg/kg bid) with a maximum of **800 mg/day (400 mg bid, if weight greater than or equal to 80 kg).**

## III. Margin of Safety Calculation

The maximum dose to be administered in this trial is **10 mg/kg/day**. CBDV safety margins estimated based on the steady state clinical exposures, indicate there is an adequate margin of safety for CBDV for the recommended maximum human daily dose of 20 mg/kg/day (administered as 10 mg/kg twice daily [bid.]) in both juvenile and adult populations.

### C.3.4. Study Drug Interruption

Dosage will be decreased or drug will be temporarily discontinued in the case of clinical or laboratory toxicity. Because of the frequency of co-morbid medical problems in this population, intolerable side effects that are symptom-based and thus subjective will be determined by the parents and investigators together on a case by case basis. The PI will make changes based on the results of side effect assessments and the physical status of the subject.

For objective measures such as weight or labs:

Measure	Toxicity criteria
1. Weight loss	>10% or excessive weight gain (determined by age, gender and familial factors) throughout the trial.
2. Clinical signs of pancreatitis and elevated lipase/amylase	2x upper limit of normal range
3. Clinical signs of liver injury with elevated bilirubin and transaminases (AST or ALT)	>8x upper limit of normal (ULN), or >5x ULN for more than 2 weeks, or >3x ULN and total bilirubin [TBL] >2x ULN, or >3x ULN and fatigue, nausea, vomiting, right upper quadrant pain/tenderness, fever, rash, and/or eosinophilia (>5%)
4. Platelets dysfunction	<80,000 /mcl
5. White blood cells dysfunction	<3.5 x 10  /mcl

Significant worsening of side effects (regardless of drug causality) (objective or subjective) for 2 consecutive visits (or phone calls) will prompt discussion with the family and may result in the discontinuation of study drug. Patient will be asked to return for a follow-up visit after early termination.

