### C.3.5 Study Drug Discontinuation

Investigators will consider terminating study participation for any subject due to any adverse event(s) (including clinically significant laboratory results) which, in the opinion of the investigator, would compromise the continued safe participation of the subject in the study. Significant non-compliance with the protocol requirements may also necessitate discontinuation. Pregnancy during study participation is an automatic criterion for permanent study drug discontinuation.

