### **C.5. Safety Assessments**

Full panel of safety labs (CBC with differential, basic metabolic panel and liver function tests) and if participant is taking one or more of the anti-epileptic medications, concomitant plasma drug levels for valproic acid, lamotrigine, oxcarbazepine, phenytoin and clobazam, which are drugs metabolized by phase 1 metabolism via CYP2C19 or CYP3A4 and phase 2 metabolism via UGT1A9 or UGT2B7, will be drawn at baseline, week 4, and week 12. Additional liver function test will be drawn at week 2 to monitor response during dose escalation. Other laboratory studies may be ordered if clinically indicated. Home medications may be monitored on a patient by patient

basis if there are safety concerns suspected to be related to a drug-drug interaction. (See Appendices A and B for the lists of drugs metabolized by phase 1 via CYP2C19 or CYP3A4 and phase 2 metabolisms via UGT1A9 or UGT2B7).

While there is no formal drug-drug interaction data to demonstrate the effect of CYP2C9 inducers and inhibitors on the PK of CBDV, PK data from study GWEP1330 does not indicate an interaction of concern. In Part A of the trial, the PK and safety of CBDV was assessed when given concomitantly with inducer AEDs (including any of the following: Carbamazepine, phenobarbital, primidone or phenytoin) and inhibitor AEDs (Valproic acid). Data indicated there were no notable differences in the safety or PK results obtained for CBDV and its metabolites between the AED groups. From a safety point of view, CYP2C9 is not the sole metabolic pathway for CBDV. CBDV may also be metabolized by other cytochrome p450 enzymes including 2C8 and 3A4. Based on this indicative data we consider the exclusion of medications that are potent inhibitors or inducers of CYP2C9 is not required.

For any clinically significant ( $>3\times$  ULN) elevation of ALT or AST, the following laboratory measures, at minimum, should be assessed within 72 hours: repeat ALT/AST, total bilirubin, alkaline phosphatase, and GGT.

Study drug will be discontinued in subjects who have:

1.  $>10\%$  Weight gain
2. Clinical signs of pancreatitis confirmed with amylase and lipase elevation  $>2\times$  ULN
3. ALT or AST  $>8\times$  ULN
4. ALT or AST  $>5\times$  ULN for more than 2 weeks
5. ALT or AST  $>3\times$  ULN and TBL  $>2\times$  ULN

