6. ALT or AST  $>3\times$  ULN with the appearance of fatigue, nausea, vomiting, right upper quadrant pain or tenderness, fever, rash, and/or eosinophilia ( $>5\%$ )

All trial subjects with elevated LFTs will be followed until all abnormalities return to the baseline state as assessed by the investigator with AST/ALT  $< 3\times$  ULN.

- Pregnancy test, if applicable, will be performed at screening, baseline, weeks 2, 4, and 12 via urine or blood
- ECG will be performed at baseline and week 12 or at the time of early termination should this arise.
- Columbia Suicide Severity Rating (C-SSRS) Scale -The Investigator will attempt to administer the Columbia Suicide Severity Rating Scale in the beginning and at each visit. If the C-SSRS cannot be performed then a clinical assessment of suicidality will be done

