#### D.3.1. Known Undesirable Drug Side Effects:

It should be noted that this investigational medication is in the early phases of development and the safety profile is yet to be established. An asymptomatic rise in transaminase levels (without rise in bilirubin levels) noted in a Phase 1 healthy volunteer multiple-dose study led to imposing a maximum dose cap of 20 mg/kg/day for CBDV. The maximum dose in this clinical trial is 10 mg/kg/day. We will screen for any evidence of acute liver failure, teratogenicity, or the occurrence of pancreatitis. It is known that certain conditions that increase the risk of the liver toxicity including: very young age (<2 years), previous liver disease, severe mental retardation/intellectual disability, the presence of an underlying metabolic disorder (especially urea cycle disorder), or organic brain disease. Participants will be pre-screened to avoid these issues (see exclusion criterion). Given the age range (5-30) it is unlikely that the teratogenicity will be an issue in this protocol since girls will not have reached menarche. Girls with menarche will be screened with a pregnancy test and excluded if it is positive.

Recently there has been evidence of increased risk of suicidal thoughts or actions in individuals taking anticonvulsant medications. Based on data analysis of 199 placebo-controlled studies of 11 antiepileptic drugs, there is a small elevated risk that occurs as early as 1 week after starting therapy and continued for at least 24 weeks. C-SSRS will be attempted to be given at each visit to identify those subjects at risk and they will be referred for therapy.

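### C.3.4 allows a dose decrease at the hepatic and pancreatitis criteria for which C.5 says study drug will be discontinued, and no text says which section governs

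*Combined protocol and SAP*

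**What the plan says.** Three sections deal with stopping or changing study drug in an individual patient.

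- **C.3.4, Study Drug Interruption.** The action is stated once, at the top: "Dosage will be decreased or drug will be temporarily discontinued in the case of clinical or laboratory toxicity". The PI makes the changes. For objective measures, a table then sets out what counts as toxicity, with rows for weight, pancreatitis, liver, platelets and white cells. The liver row is headed "Clinical signs of liver injury with elevated bilirubin and transaminases (AST or ALT" and gives four ALT/AST cut-offs. A closing paragraph adds that significant worsening over two consecutive contacts "will prompt discussion with the family and may result in the discontinuation of study drug".
- **C.5, Safety Assessments.** A list of six criteria follows the words "Study drug will be discontinued in subjects who have". One concerns weight gain, one pancreatitis and four ALT/AST. The last of these is ALT or AST >3x ULN "with the appearance of fatigue, nausea, vomiting, right upper quadrant pain or tenderness, fever, rash, and/or eosinophilia" (>5%). On follow-up, C.5 says: "All trial subjects with elevated LFTs will be followed until all abnormalities return to the baseline state as assessed by the investigator", with AST/ALT <3x ULN.
- **C.3.5, Study Drug Discontinuation.** Investigators are to consider ending participation for adverse events, including laboratory results, that in their opinion compromise safety. Only one event is made automatic and permanent: "Pregnancy during study participation is an automatic criterion for permanent study drug discontinuation".

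**The concern.** The same laboratory result can fall under two instructions. At ALT/AST >3x ULN with total bilirubin >2x ULN, for example, C.5 requires study drug to stop, while C.3.4 offers a lower dose as one of two acceptable responses. This is not a tiered scheme, in which reduction would start at a lower threshold than stopping: the hepatic thresholds are identical.

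The matter is one of patient safety. Transaminase elevation is the drug's identified liver signal and the reason for its 20 mg/kg/day cap (D.3.1). Participants may be as young as 5, and some may take valproic acid or other antiepileptics. After week 4 the next scheduled liver panel is at week 12. A patient kept on a reduced dose in between would rely on event-driven testing.

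**Working it through.** No figure in the plan has to be reproduced. The check is a comparison of the two lists, followed by a search for any text that reconciles them.

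**Step 1. Criteria side by side.** In the last column the C.3.4 liver heading is read literally, so a patient must have clinical signs, raised bilirubin and raised transaminases.

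| C.5 stop criterion | Counterpart in C.3.4 | Overlap if heading is a label | Overlap if heading is literal |
|---|---|---|---|
| 1. Weight gain >10% | Excessive gain, no percentage given | Not counted | Not counted |
| 2. Clinical pancreatitis, amylase and lipase >2x ULN | Clinical pancreatitis, lipase/amylase 2x ULN | Yes | Always |
| 3. ALT/AST >8x ULN | Same cut-off | Yes | Only with clinical signs and raised bilirubin |
| 4. ALT/AST >5x ULN for more than 2 weeks | Same cut-off | Yes | Only with clinical signs and raised bilirubin |
| 5. ALT/AST >3x ULN and bilirubin >2x ULN | Same cut-offs | Yes | Only with clinical signs as well |
| 6. ALT/AST >3x ULN with symptoms or eosinophilia | Same cut-off and list | Yes | Only with raised bilirubin as well; eosinophilia alone is not a clinical sign |

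**Step 2. Count.** With the heading as a label, overlap is 1 (pancreatitis) + 4 (hepatic) = 5 of 6. Read literally, 1 of 6 always overlaps and the 4 hepatic criteria overlap conditionally. These are counts of wording, not of risk; the documents give no event frequencies.

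**Step 3. Which actions comply with both sections?**

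- Temporary stop: allowed by C.3.4. It can be squared with C.5, which does not say that its stop is permanent.
- Dose decrease: allowed by C.3.4. It does not comply with C.5.

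Stopping is therefore the only action that satisfies both.

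**Step 4. Does any text settle precedence?** C.3.4 and C.5 do not cross-refer. C.3.5 is discretionary except for pregnancy. The closing paragraph of C.3.4 says only that discontinuation may result. The follow-up sentence in C.5 governs monitoring and is silent on dosing. None of these says which section prevails.

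**Step 5. Practical reach.** The scheduled safety panel in C.5 is CBC, basic metabolic panel and liver function tests. Amylase and lipase are not in it, so the pancreatitis overlap arises only on unscheduled testing. The hepatic overlap can arise from scheduled liver tests.

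**The case against.** The strongest reply is that the sections can be read together. C.3.4 states a general choice of actions, and its table assigns no action to individual rows. C.5 states a specific, mandatory action for a subset. On the usual principle the specific rule narrows the general one, and dose decrease still has work to do for platelets, white cells, weight loss and subjective side effects. A cautious investigator would stop the drug. This reading is sensible, but the protocol does not state it. It leads to the same place as Step 3: stopping is the one compliant action, and C.3.4 should say so.

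The second reply is that safeguards exist. Directly before its stop list, C.5 asks for repeat ALT/AST, total bilirubin, alkaline phosphatase and GGT within 72 hours of any ALT/AST above 3x ULN. C.3.5 allows termination for safety, the safety committee can recommend stopping the study, and the Research Monitor can remove subjects. This stands, and it lowers the consequence. None of these provisions resolves what happens to the dose at the shared cut-offs.

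The third reply concerns extent, and it also stands. A reader might infer that the conflict covers the signal described in D.3.1: "An asymptomatic rise in transaminase levels (without rise in bilirubin levels) noted in a Phase 1 healthy volunteer multiple-dose study". Read literally, the C.3.4 liver heading leaves such a patient out, so only C.5's stop would apply at its >8x ULN cut-off or its >5x ULN cut-off for more than 2 weeks. The overlap reaches that patient only if the heading is a label.

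A reader might also treat the lack of a restart rule as a defect in its own right. The word for a temporary stop does imply resumption, and no condition is written. But C.3.4 leaves dose changes to the PI, and in a single-site, 12-week pilot of 36 participants that is defensible. It is an optional clarification.

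**Conclusion.** The inconsistency is real and should be fixed. For criteria that appear in both sections, C.3.4 permits a dose decrease that C.5 does not allow, and no text says which governs. The extent is 5 of C.5's 6 criteria if the C.3.4 liver heading is a label. If the heading is literal, only pancreatitis always overlaps, and the hepatic criteria overlap only in patients who also meet it. The documents do not say which reading is meant, and that uncertainty is part of the problem.

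The conclusion assumes that the opening action of C.3.4 applies to the toxicity criteria tabulated beneath it, which is the natural reading of that section. It does not mean that the protocol lacks a mandatory liver stopping rule, since C.5 contains one, or that it directs continued dosing in liver injury. No effect on the week-12 comparison is claimed, because nothing in the documents indicates how often these criteria would be met.

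**What to change.** Amend the wording of C.3.4 in three places:

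1. State that its hepatic and pancreatitis criteria require study drug to be stopped as in C.5.
2. Remove the dose-decrease option for those rows only, keeping it for the other toxicities.
3. Rename the liver row *ALT/AST elevation*, so that both sections use the same trigger and an asymptomatic rise is treated alike in each.

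Optionally, say in C.5 whether the stop is permanent or on what condition drug may be restarted.

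The cost is amendment text, with no new assessments. The downside is slightly less investigator discretion to lower the dose instead of stopping at these cut-offs.

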#### VII. Dietary Diary

Dietary intake will be assessed using the National Cancer Institute (NCI) 24-hour automated recall method, which will be completed by the primary caregiver in 15 to 20 minutes. Dietary recalls will be obtained to assess pre-treatment dietary habits at baseline, and assessed at monthly interval during in person visits at weeks 4, 8, and 12. The NCI nutritional program output will allow for secondary analyses of impact of treatment on both dietary macronutrient ratio (percent carbohydrates, proteins and fats) and caloric intake.

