#### **C.9.2. Study Visit Details:**

Study visits are divided into remote and in-person visits. Remote visits are done via tele-medicine and utilizing patient’s local Quest labs. In person visits are conducted at the Montefiore/Einstein site and on-site clinical research center.

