### **IV. Visits 2 to 6 (weeks 2, 4, 6, 8 and 10, remote)**

Participants will be followed remotely by the clinical team at weeks 2, 4, 6, 8 and 10. The clinicians will review with patients about any interval changes, including changes to any concomitant medications and development of any adverse events. Patient will be assessed for suicidality using C-SSRS. Menstrual diaries will be reviewed if applicable. At weeks 2 and 4, patient will be scheduled and requested to go to a local Quest lab for blood work. No lab test is required for weeks 6, 8 and 10 after patient has reached steady maintenance dose and liver function had been checked

at prior visits. Rating forms will be provided to patients in hardcopies at baseline visits and electronic copies will be provided by email. Participants would be provided Fedex labels and envelopes to return the rating forms. Drug dispensing at Week 4 and Week 8 will occur after clinician safety assessments and IP supply will be Fedex to study participants by the Investigational Drug Service Pharmacy

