## C.10. Schedule of Events

Procedure	Time Needed	Completed By			Screening (Remote)	Baseline (On Site)	Wk 2 (Remote)	Wk 4 (Remote)	Wk 6 (Remote)	Wk 8 (Remote)	Wk 10 (Remote)	Wk 12 / Early Term (On Site)	Wk 14 F/U (Remote)
		Parent	Child	Clinician									
Informed Consent	60 min	X	X	X	X	X							
I/E Criteria	10 min	X		X	X	X							
Medical Hx/Demographic	30 min	X		X	X								
Physical/Neuro Exam	20 min		X	X		X						X	
Psychiatric Interview	30 min	X	X	X	X								
IQ test (SB-5, Abbreviated)	20 min	X	X	X		X							
ECG	20 min		X	X		X						X	
Randomization	0 min					X							
Review Concomitant Medications	5 min	X		X	X	X	X	X	X	X	X	X	X
Drug Test	5 min		X		X*	X							
Pregnancy Test (if applicable)	5 min		X		X*	X		X*				X	
Vital signs, Weight, BMI	15 min		X	X		X						X	
CBC with differential and basic metabolic panel	15 min		X		X*	X		X*				X	
Liver Function Enzymes	15 min		X		X*	X	X*	X*				X	
AED drug levels (if applicable)	15 min		X			X		X				X	
Adverse Event Monitoring	10 min	X		X			X	X	X	X	X	X	X
Menstrual Diary Review (if applicable)	5 min	X				X		X		X		X	
Dispense Medication	5 min	X		X		X		X		X			

Scales	ABC-I	15 min	X			X	X		X		X		X	X
	RBS-R	20 min	X				X		X		X		X	
	CSQ	15 min	X				X		X		X		X	
	CY-BOCS	20 min	X		X		X		X		X		X	X
	HQ-CTx	15 min	X		X		X		X		X		X	X
	MERS-R-PWS	15 min	X		X		X		X		X		X	X
	CGI-I	5 min		X	X				X		X		X	X
	CGI-S	5 min		X	X	X	X		X		X		X	X
	C-SSRS	15 min	X	X	X		X	X	X	X	X	X	X	X
	Dietary Diary	15 mins	X				X		X		X		X	
	Actigraphy **	ongoing	X	X	X		X						X	

\*Denotes visit require outpatient Quest visit

\*\*Actigraphy device will be dispensed to participants after successful screening and prior to baseline visit, will collect minimum of 3 days of baseline data prior to randomization. Information collected continuously and reviewed at in person visit

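### The 10% weight rules have no scheduled on-treatment weight to act on between Baseline and Week 12/Early Termination

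*Combined protocol and SAP*

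**What the plan says.** **The rules.** C.3.4 groups weight with laboratory values as an objective measure. It gives loss above 10%, or "excessive weight gain (determined by age, gender and familial factors) throughout the trial", as grounds for lowering the dose or pausing drug. C.5 is mandatory: "Study drug will be discontinued in subjects who have" any of six findings, the first being weight gain above 10%.

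**The measurements.** In C.10 the row "Vital signs, Weight, BMI" is marked at Baseline and Week 12/Early Termination only. C.9.2 IV says "Participants will be followed remotely by the clinical team at weeks 2, 4, 6, 8 and 10". At those contacts "The clinicians will review with patients about any interval changes, including changes to any concomitant medications and development of any adverse events". The section also covers suicidality, menstrual diaries, laboratory visits, rating forms and drug supply, but no weight. On resupply it says "Drug dispensing at Week 4 and Week 8 will occur after clinician safety assessments".

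**The conflicts.** C.8.3 says the dietary recall is "assessed at monthly interval during in person visits at weeks 4, 8, and 12", whereas C.9.2 IV and C.10 make weeks 4 and 8 remote, and C.9.2 explains that "Remote visits are done via tele-medicine". C.9.2 V, the Week 12 visit, states that weight is measured at every visit, which neither the schedule nor the remote-visit text supports.

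**The concern.** A stopping rule stated as a percentage change needs a measurement while there is still treatment to stop. If a site follows the schedule, the first weight after Baseline comes at the visit where planned dosing ends. An Early Termination weight does not help, because it is taken after the decision to stop.

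At stake is participant safety. The trial enrols from age 5, hyperphagia is a feature of the syndrome (Section B), and D.3.1 says the drug's safety profile is not yet established. The protocol writes weight rules in both directions, so it treats weight change as something to act on.

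The conflicting statements add a practical problem. A reader of C.8.3 and the Week 12 text would expect interim weights; a reader of C.9.2 IV and C.10 would not.

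**Working it through.** The plan gives no figure on this point to reproduce. The check is a count from the schedule, a reading of the text beside it, and a small calculation for the fix.

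**1. Scheduled weights (C.10).**
- Marked visits: Baseline and Week 12/Early Termination, so 2.
- Weeks 2, 4, 6, 8 and 10: 0 of 5.
- Adverse event monitoring at the same five contacts: 5 of 5.

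**2. Longest interval without a scheduled weight**, taking Baseline as week 0.
- C.9.2 IV and C.10 as written: 12 − 0 = 12 weeks.
- If weeks 4 and 8 were in person with weight taken (C.8.3 read with the Week 12 text), or with home weights added at weeks 4 and 8: max(4 − 0, 8 − 4, 12 − 8) = 4 weeks.

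**3. Which reading governs.** C.9.2 IV, its visit heading and the column labels in C.10 all make weeks 4 and 8 remote, and C.9.2 describes remote visits as telemedicine. The contrary statements are one clause in the dietary diary section and one sentence in the Week 12 section. The remote reading is the more likely one, and under it no interim weight is scheduled.

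**4. Comparison with other objective criteria.** C.5 and C.10 schedule liver tests at weeks 2 and 4 and a blood count at week 4. The pancreatitis rule is triggered by clinical signs. The weight rules need no clinical sign and have no measurement before treatment ends.

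**5. The two weight rules side by side.**

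| | Loss | Gain | Action |
|---|---|---|---|
| C.3.4 | above 10% | excessive, no number | reduce or interrupt |
| C.5 | none | above 10% | discontinue |

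**6. What a home scale can support.** Let W be starting weight and e the largest error in the home-measured change. A true 10% change reads at least (0.10W − e)/W; no change can read as much as e/W. The documents give no value for e, so e = 1 kg is an assumption, and the weights are illustrative.

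| W | Lowest reading for a true 10% change | Highest reading for no change |
|---|---|---|
| 20 kg | (2 − 1)/20 = 5% | 1/20 = 5% |
| 40 kg | (4 − 1)/40 = 7.5% | 1/40 = 2.5% |
| 80 kg | (8 − 1)/80 = 8.75% | 1/80 = 1.25% |

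A trigger separates the two cases only if e/W < (0.10W − e)/W, that is, e < W/20: below 1 kg at 20 kg, 2 kg at 40 kg and 4 kg at 80 kg. In the smallest children a trigger low enough to catch every true 10% change may also fire on error alone. Hence the confirmatory weight, and the use of one scale throughout so that a constant offset cancels.

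**The case against.** The strongest reply is that participants are not unobserved. A clinician reviews them every two weeks, drug at weeks 4 and 8 is released only after a safety assessment, and the dietary diary and hyperphagia questionnaire are scheduled at those same weeks. C.3.4 also lets the investigator act on the participant's physical status and on worsening at two consecutive contacts. All of this stands as partial mitigation: any of it could prompt a weight check. None of it yields a number to set against 10%, and C.3.4 itself separates weight from the symptom-based effects judged case by case.

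A second reply is that this is a drafting conflict, since the Week 12 text has weight taken at every visit. That is why the consequence is limited to the schedule as written. The conflict needs correcting on either reading.

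Third, the C.3.4 wording may mean cumulative change over the trial rather than repeated weighing. That is fair, but the mandatory rule in C.5 does not depend on that phrase.

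Two stronger readings are tempting. One is that participants will pass 10% unnoticed, or that the drug is known to affect weight. The documents do not support this: they give no rate of such change, D.3.1 names no weight effect, and clinicians are in regular contact. The other is that lipase and amylase are an equal gap, because exclusion 8 limits both to twice the upper limit of normal while no scheduled panel names either. But exclusion 8 opens by referring to clinical indications, the pancreatitis rules are sign-triggered, and for-cause tests are allowed, so a symptom-led check is a consistent reading. That is a minor wording note only.

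**Conclusion.** The point holds for the schedule as written: no weight at any of five on-treatment contacts, and 12 weeks in which the weight rules in C.3.4 and C.5 have no scheduled measurement to act on. This rests on weeks 4 and 8 being remote, which the visit text and schedule support and the dietary diary section contradicts. Existing reviews soften the gap without closing it.

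How many of the 36 participants would be affected cannot be estimated from the documents. The primary endpoint, sample size and power are untouched. This is a safety-monitoring gap that should be closed, with high confidence in the scheduling facts and no claim about how often harm would follow.

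**What to change.** 1. Obtain a home-scale reference weight at or just before the first dose.
2. At weeks 4 and 8, record a caregiver-reported weight on the same scale before drug is dispensed.
3. State a trigger below 10%, chosen by the investigator with allowance for scale error in small children. Reaching it prompts a confirmatory weight on a calibrated scale, for example at a local clinic, compared with the clinic Baseline weight.
4. Add these steps to C.9.2 IV and the weight row of C.10. Correct the visit mode in the dietary diary section and the every-visit statement in the Week 12 section.
5. Make the thresholds in C.3.4 and C.5 agree: one numeric limit for gain, and a clear statement of what follows from loss.
6. Minor: either add lipase and amylase to the screening draw, or say in exclusion 8 that they are tested only when clinically indicated.

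The cost is one reference weight, one question at two existing contacts, an occasional local trip and amendment wording; the documents give no prices. The downsides are home-scale error and some false triggers, mostly in the lightest participants. If the enzymes are added, two assays on blood already drawn may cause a few extra screen failures in a rare-disease trial.
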